**SECTION B: FUNDING**

Provide information regarding **ALL** funding sources in this section. This includes **ANY EXISTING FUNDING, PENDING FUNDING, OR FUNDING THAT HAS BEEN APPLIED FOR TO SUPPORT THIS RESEARCH.**

Please check all that apply:	
	This research is funded
Have you received Just In Time (JIT) Notification?  Yes  No	

	Funding has been requested Have you received Just In Time (JIT) Notification?  Yes  No
NOTE: Once the funding has been awarded, submit an amendment to the IRB to add the funding source	
	Research is not funded

**If the research is funded or funding has been requested, it is REQUIRED that you complete the box below. The Sponsor Award # must be included in the box below. If you don't have an award #, please state that in the box below. If you have multiple funding sources, add additional boxes as necessary.**

Sponsor Name		National Institute on Alcohol Abuse and Alcoholism (NIAAA)
Title of Grant/Proposal		Interdisciplinary Study of Two Novel Anticonvulsants in Alcoholism
Sponsor Award # (REQUIRED)* *If Award # is pending, put pending. Once the funding has been awarded, submit an amendment to the IRB to add the funding source		2R01AA015923-06
YES	NO	
		Is Boston University the Prime Awardee of the grant?
		Is Boston University receiving a sub-award? Name of Prime Recipient: N/A

**\*NOTE:** Provide a copy of the grant application, funding proposal, scope of work, or sub-award agreement. The University is required to verify that all funding proposals and grants have been reviewed by the IRB before funds are awarded.

If this research study is for your dissertation, provide a copy of your prospectus (if available).

### **SECTION C: CONFLICT OF INTEREST**

 YES (REQUIRED)	I confirm that all those responsible for the design, conduct, or reporting of the proposed program, including at minimum, all Senior/key personnel in the grant application, have completed the financial interest disclosure forms, submitted them to the COI office, and completed training as dictated at: http://www.bu.edu/orc/programs-committees/coi/ , and as provided under the Boston University Policy on Investigator's Conflicts of Interest .
Of the financial interest disclosure forms submitted, has anyone checked "yes" to any of the questions on either the FIND1 or NONFIND1 form?	

 Yes*	 No
-------------------------------	--

**\*If anyone checked “yes” to any of the questions on either the FIND1 or NONFIND1 form, the IRB Director will contact the COI office to obtain the disclosure information.**

#### **SECTION D: TYPE OF REVIEW**

For Guidance regarding Type of Review please refer to the following website:

<http://www.bu.edu/irb/guidance-and-faqs/submission-guidance/difference-between-exempt-expedited-and-full-board>

##### **I. FULL BOARD**

Please refer to the IRB website for Full Board submission deadlines and meeting dates:

<http://www.bu.edu/irb/about-us/meeting-dates/>

**Note: The IRB will make the final determination on the Type of Review**

**\*Minimal risk** means that the probability and magnitude of harm or discomfort anticipated in the research are not greater in and of themselves than those ordinarily encountered in daily life or during the performance of routine physical or psychological examinations or tests.

**Note: Section E of this application, which includes study team members, was removed from this document prior to submission to ClinicalTrials.gov. The names and training dates of study team members are not necessary to evaluate study procedures or methods.**

## **SECTION G: STUDY SUMMARY**

**Summarize the study in lay language (do not copy from the grant/scope of work/proposal, etc.). This summary should include the research design, purpose, objectives, research question, hypothesis, and any relevant background information.**

**Note: Do not include a list of citations in this section. Please limit this section to no more than 300 words.**

Alcoholism is the third leading cause of preventable death in the US, accounting for 80,000 deaths annually. Almost 18 million US adults have alcohol use disorder (AUD); however, approved medications for the treatment of AUD has shown limited effectiveness.

Zonisamide (ZON), a broad spectrum anticonvulsant, has proven to be more effective than a placebo in reducing alcohol intake in individuals with alcohol dependence. ZON’s mechanism of action seems to be quite distinct from currently approved anti-alcoholism medications, which holds promise for treatment of individuals who are not responsive to conventional medications.

However, much remains unknown about ZON's therapeutic mechanisms and ZON's efficacy in treating patients with a diagnosis of AUD.

To fill in these gaps, we will conduct a double-blind randomized controlled study that assesses ZON's treatment mechanisms and effectiveness in reducing alcohol consumption in patients with AUD. Participants will be randomized to one of two conditions: 1) treatment with ZON and a computerized alcohol reduction and medication compliance program called *Take Control* (TC); 2) treatment with a placebo (PLC) and TC. To understand the neurobiology behind ZON's potential therapeutic effects on AUD, fMRI will be acquired at baseline (pre-treatment) and near the end of study treatment and used to compare the brain activity of the ZON+TC versus PLC+TC group while they perform an alcohol and emotional-word Stroop task, as well as an alcohol related cues task.

Compared to the PLC+TC group, we hypothesize that the ZON+TC group will: 1) have significantly greater reductions in alcohol consumption by the end of a 12-week treatment period; 2) show enhanced midbrain-frontal connectivity while performing the Stroop task during an fMRI procedure; and 3) decreased limbic and prefrontal activity during an alcohol cues task.

#### **SECTION H: RESEARCH METHODS AND ACTIVITIES (Check all that apply)**

	Collection of audio, video, digital, or image recordings
	Biological samples → Complete Biological Samples Form: http://www.bu.edu/irb/application-forms/ Examples: blood, hair, cheek swab, urine, tears, saliva, etc.
	Collection of data that may be sensitive and if disclosed could put subjects at risk for legal or social harms. Examples: Illegal behaviors, HIV status, psychiatric illness, information related to sexual behaviors, etc.
	Coordinating Center/Lead Site
	Deception
	Devices → Complete Devices Form: http://www.bu.edu/irb/application-forms/
	Drugs → Complete Drugs Form: http://www.bu.edu/irb/application-forms/
	Ethnographic: The study of people in their own environment through the use of methods such as participant observation and face-to-face interviewing
	Focus Groups
	Genetics Testing → Complete Genetics Form: http://www.bu.edu/irb/application-forms/

	MRI
	Placebo
	Pregnancy Testing
	Randomization
	Surveys, interviews, questionnaires
	Secondary Data Analysis
	Other (please describe):

### **SECTION I: SUBJECT POPULATION**

Number of Subjects to be Enrolled:
 
If you have sub-groups or more than one arm, please separate out these enrollment numbers.
 
Note: Please account for subjects who may drop out or be withdrawn from the study. Any subject who signs a consent form is considered to be enrolled regardless of whether they complete any study procedures
	
Total of 180 Enrolled
 
Total 100 Randomized:
 
 
- Target Male:Female ratio 55:45
 
- Target number per treatment arm: 
 
- PLC+TC: 50
 
- ZON+TC: 50
 
 
 
 
AUD is far more common in men than in women. Our proposed enrollment gender ratio reflects this difference in prevalence.

---	---

Check all categories that apply to your target population:	
	Adults
	Children (< 18 years of age)
	Cognitively-Impaired Adults
	Non-English Speaking

	Prisoners
	BU Employees
	BU Students
	Wards of the state
	Other (please describe):

**If Categories other than 'Adult' are checked, describe the additional safeguards that have been put in place to protect that subject population. For Cognitively-Impaired Subjects, provide the rationale for including this population in this research study.**

N/A

### Eligibility Criteria

Inclusion Criteria:

- 1) DSM-5 diagnosis of an Alcohol Use Disorder (AUD)
- 2) Adults ages 21 to 65 years old
- 3) Expressed desire to stop drinking alcohol completely or to reduce alcohol consumption
- 4) Reported drinking an average of at least 14 standard drinks per week for males, or 7 for females occurring over a 28-consecutive day period during the 90 day-long time window that preceded the screening session
- 5) Must be willing to discontinue psychotherapy for substance use disorder (except A.A. session attendance)

Exclusion Criteria (exclusion criteria are the specific criteria which would disqualify an individual from participating in the study, not simply the opposite of the inclusion criteria):

Exclusion from Recruitment:

- 1) Bipolar disorder, schizophrenia, current bulimia/anorexia, dementia, or other substance use disorder, with the exception of nicotine, marijuana, and caffeine.
- 2) Clear and current suicidal risk. Subjects who are determined by either the medical team or PI to be at moderate to high risk of suicide (as evidenced by reports of the following: persistent thoughts about how one might kill themselves, intentions of acting on thoughts of killing themselves, making plans to kill themselves, making preparations to kill themselves, a suicide attempt in the past year, or 2 or more hospitalizations due to depression within the past 5 years) will be excluded from recruitment.
- 3) Significant medical problem (e.g. uncontrolled diabetes, cancer, uncontrolled hypertension) or neurological conditions (e.g., seizures, dementia, PD) that in a clinical context would require prioritization for immediate treatment or simultaneous treatment that could interact with the study treatment in unknown ways.

4) Medical contraindication to the use of ZON, as indicated by the FDA Zonisamide medication guide. These include history of significant renal disease or current renal impairment (as indicated by creatinine levels greater than 2.0 mg per dL in females and 2.5 mg per dL in males), kidney stones, liver problems (as indicated by AST/ALT outside of normal limits), and evidence of metabolic acidosis (as indicated by serum or plasma bicarbonate < 22 mmol/L)

*Note:* Following randomization, treatment will be discontinued under the authority of the study physician if there is evidence of metabolic acidosis, acute renal injury (>threefold increase in serum creatinine levels from baseline) or a significant change in liver function (AST or ALT > 3X UNL for more than two weeks).

- 5) History of anticonvulsant-induced rash
- 6) Currently taking:
  - a. acamprosate, naltrexone, topiramate, disulfiram, or benzodiazepines
  - b. a medication that is a moderate or major inducer of cytochrome P450 3A4 enzymes
  - c. an amphetamine or other psychomotor stimulant
  - d. opioids or have been treated chronically with opioids
  - e. antipsychotic agents, anticonvulsants, or sedative hypnotics
  - f. drugs with “sulfa” moiety (e.g. sulfonamides, sulfonylureas, carbonic anhydrase inhibitors, thiazides, and loop diuretics), except ethacrynic acid
- 7) Previously received ZON for the treatment of an AUD
- 8) Known allergy to sulfonamides
- 9) Implantation of anything containing magnetically sensitive material including metal plates, aneurysm clips, and cardiac pacemakers, stents; history of sheet metal work, claustrophobia
- 10) Non-English speakers
- 11) Women who are trying to become pregnant, pregnant women or women who are lactating (breastfeeding)

*Note:* Women of child bearing potential (not postmenopausal for at least one year) will only be admitted into this study if they are found to have a negative HCG test during screening and agree to use of an effective means of contraception during the course of the study. Acceptable forms of birth control include one or more of the following: tubal sterilization, partner’s vasectomy, intrauterine device, hormonal birth control pills, hormonal skin patch, hormonal vaginal ring, hormonal under-the-skin implants, and hormone shots. Condoms, considered a less reliable method of birth control, must be paired with one of the above reliable forms.

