All medication records and dispensing will be managed by the nurse administrator. Pills will match the placebo. Based on previous findings (Knapp et al., 2015), ZON dose of 400 mg daily will be used as the target maintenance dose in this study. A final target maintenance ZON dose of 400 mg will be given after a seven week long titration period. Based on the known half-life of ZON, it is expected that it will take approximately 2 weeks to reach steady state for a given dose of ZON. Participants will begin the medication taper schedule at week 12. According to this schedule, participants will be reduced to a dosage of 300 mg for the entirety of week 12, reduced to a dosage of 200 mg for the first three days of week 13, reduced to a dosage of 100 mg for the next three days, and then the participant will be done taking the medication. Therefore, the participant will be completely off of the medication by the day before the week 14 session. Pill placebo will be administered according to the Zonisamide schedule.

Dosage escalation and maintenance regimen

Week 1 + 2	Week 3 + 4	Week 5 + 6	Week 7 – 12 Maintenance
100 mg/day (once a day)	200 mg/day (once a day)	300 mg/day (once a day)	400 mg/day (once a day or two divided doses)

Dosing will be modified, if needed, to adjust for subject tolerance of drug dosing or to reduce adverse drug effects. Verification of medication adherence compliance will entail comparing the patient’s self-report against the number of pills remaining in the medication vial. Pill counts will be conducted at each visit to encourage medication adherence.

Medication will be dispensed according to a two-week dosing schedule by medical personnel at weekly study sessions. Participants will be supplied with two medication bottles at each study visit, containing between 4-7 days of medication in one bottle and 7 days of medication in the other. At any given time, participants may have between 10-17 days of medication in two or three medication bottles. Patients will self-administer medications daily, as directed.

Patients who have to discontinue medication will be permitted to remain in the study and participate in study assessments and will be allowed to continue to receive TC.

Participants who are withdrawn from the study will be tapered off the medication. Any unused medication can be returned during the taper period, either in person or by a postage-paid return envelope we will supply them with.

II. Take Control:

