**Risk of loss of confidentiality**

The investigator and his staff will take every precaution to maintain subject confidentiality; however, there is always the possibility that confidentiality may be broken.

**Describe the plan to minimize risks. Include in the description the availability of any medical or psychological resources.**

The overriding concern of the investigators is the safety of the subjects who participate in this study. Participants will be informed about all risks and told that they may withdraw from the study at any time and may refuse to complete any treatment procedures. Study personnel will be monitoring the patients' clinical condition carefully and constantly and will withdraw patients from the study if their clinical condition warrants.

In order to minimize risks, patients with prominent suicidal ideation (assessed as part of the clinical interviews, including the MINI, and with the self-monitoring forms) will be excluded. Treatment will be closely monitored by the PI in weekly supervision meetings. The MINI Suicidality interview will be used to measure participants' suicidality scores during the screening session, and will be administered to measure suicidality at every session during clinic visits, and at follow up by phone. A significant increase in depression is defined by scoring at least 10 points higher than baseline on the BDI-II, and getting a total scoring of at least 17. Clinical judgement by the study physician or associated licensed psychologist will be used to decide whether a suicidal potential has developed. The clinical case of any patient showing significant increases in depression symptoms or developing suicidal potential will be reviewed by the PI. These patients will be asked to withdraw from the protocol and given or referred to immediate clinical intervention. Appropriate protective factors and safety plan will be followed based on the attached document, if the patient reports suicidal thoughts with high levels of intent

with a specific plan/access, or regardless of plan. Additionally, all patients will be clearly informed of their right to withdraw from the study at any point.

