#### Zonisamide

In order to minimize potential side effects of ZON, subjects who can be expected to experience any severe side effects will be excluded from the study by the screening procedures. Laboratory values for relevant blood chemistry will be collected at screening and approximately every two weeks during the acute treatment period. Treatment will be discontinued under the authority of the study physician if there is evidence of metabolic acidosis, acute renal injury ( $>3$ fold increase in serum creatinine levels from baseline) or a significant change in liver function (AST or ALT  $> 3$ X UNL for more than two weeks). A physician will be available on-call at all times to answer medical questions or to assess subjects for potential medical problems or untoward effects due to their participation in the study. In addition, participants will carry an alert card on their person, explaining the effects of the study medications and a 24-hour phone number to call, in case of emergency. Should a subject experience a severe adverse drug reaction, they will receive an evaluation by a physician. Symptoms may become severe enough to require hospitalization in order to be managed safely and assistance with withdrawal will be readily available during all phases of treatment. If management of withdrawal is necessary, subjects will be evaluated and treated at a local emergency facility. However, no special provision will be made for compensation or for payment for treatment solely because of their participation in this study.

The dosage regimen selected for the administration of Zonisamide in this study (target maintenance dose of 400 mg per day) was selected based on our experience with this drug in treating alcohol-dependent subjects. The Take Control alcohol reduction and medication compliance program has been tested in one of our completed multisite clinical trial and is currently being used in a second NIAAA sponsored multisite medication trial.

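### The only creatinine-triggered stop is a more than threefold rise from baseline; at baselines above 0.67 (women) or 0.83 mg/dL (men), creatinine can pass the protocol's own contraindication level first

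*Combined protocol and SAP*

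**What the plan says.** Exclusion 4 in Section I (Eligibility Criteria) sets out medical contraindications to zonisamide. Renal impairment is among them, indicated by "creatinine levels greater than 2.0 mg per dL in females and 2.5 mg per dL in males". The note that follows covers the period after randomization and requires discontinuation for three findings. One is metabolic acidosis. The renal finding is worded as "acute renal injury (>threefold increase in serum creatinine levels from baseline"). The third concerns the liver and is put as "a significant change in liver function (AST or ALT > 3X UNL for more than two weeks").

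The Zonisamide paragraph of Section M repeats the rule: "Treatment will be discontinued under the authority of the study physician if there is evidence of metabolic acidosis, acute renal injury", again defined by a more than threefold rise. On sampling it says: "Laboratory values for relevant blood chemistry will be collected at screening and approximately every two weeks during the acute treatment period".

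Two other provisions allow action on clinical grounds. The risk-minimization text in Section M says that staff "will withdraw patients from the study if their clinical condition warrants". The dosing text in Section L (Study Sessions) says: "Dosing will be modified, if needed, to adjust for subject tolerance of drug dosing or to reduce adverse drug effects". Neither names a creatinine value. The documents give no absolute creatinine level on treatment, no hold, no rule for a repeat test and no dose reduction based on creatinine.

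**The concern.** The entry limit is absolute and the on-treatment limit is purely relative. A participant whose creatinine rises during treatment can therefore reach a value that the protocol treats as a reason not to give zonisamide, without meeting the rule that requires it to be stopped. The distance between the two levels grows with baseline creatinine, so the participants who start highest have the latest required stop.

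What is at stake is patient safety in a small number of people. Section M itself describes kidney stones, metabolic acidosis and renal tubular acidosis with this drug. No efficacy endpoint or analysis is involved.

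**Working it through.** **Inputs.** The contraindication level L is 2.0 mg/dL for women and 2.5 mg/dL for men (Section I, exclusion 4). The stop applies when creatinine exceeds 3b, where b is the participant's baseline (Section I, note to exclusion 4; Section M, Zonisamide). The documents report no baseline creatinine values, so every b below is an assumption.

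**Break-even baseline.** Creatinine passes L before the stop applies whenever 3b > L, that is, when b > L/3.

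- Women: 2.0/3 = 0.67 mg/dL.
- Men: 2.5/3 = 0.83 mg/dL.

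Below these values the relative rule acts first. A woman at 0.6 must stop above 3 × 0.6 = 1.8, and a man at 0.8 above 3 × 0.8 = 2.4. There is no gap for either.

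**Size of the gap above break-even.** The gap is 3b − L. The fold rise at which L is reached is L/b.

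| Sex | Assumed b (mg/dL) | Stop required above, 3b | Gap past L | Fold rise at L |
|---|---|---|---|---|
| Women | 0.7 | 2.1 | 0.1 | 2.86 |
| Women | 0.8 | 2.4 | 0.4 | 2.50 |
| Women | 0.9 | 2.7 | 0.7 | 2.22 |
| Women | 1.0 | 3.0 | 1.0 | 2.00 |
| Men | 0.9 | 2.7 | 0.2 | 2.78 |
| Men | 1.0 | 3.0 | 0.5 | 2.50 |
| Men | 1.1 | 3.3 | 0.8 | 2.27 |
| Men | 1.2 | 3.6 | 1.1 | 2.08 |

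**Upper bound.** The numeric entry limit alone would admit baselines up to 2.0 (women) and 2.5 (men). The required stop there would be above 3 × 2.0 = 6.0 and 3 × 2.5 = 7.5 mg/dL. These are limits of the arithmetic, not expected cases.

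**With an absolute level added.** The trigger becomes the smaller of 3b and L. At b = 1.0 it falls from 3.0 to 2.0 (women) or 2.5 (men). At or below break-even nothing changes.

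**The case against.** There is a fair case on the other side.

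- **A looser stop than entry limit is normal.** Exclusion criteria are meant to be cautious, and a fold change is a legitimate definition of acute injury. The liver rule has the same shape: entry excludes "liver problems (as indicated by AST/ALT outside of normal limits"), while the stop comes only above three times the upper limit, sustained for more than two weeks. This stands, and a mismatch between the two limits is not an error in itself. The difference is that the liver ceiling is fixed to a reference limit, whereas the renal one moves with the participant's baseline.
- **Other provisions already require action.** Withdrawal on clinical grounds is worded as something staff will do, not something they may do. Metabolic acidosis is a mandatory stop in the same sentence as the renal rule, and bicarbonate is among the chemistries measured. Section R also gives expedited review to events judged a contraindication or significant hazard. These narrow the gap. However, the first depends on judgement, the second responds to a different finding, and the third leads to review and reporting rather than a hold.
- **The situation should be rare.** Exclusion 4 removes a history of significant renal disease, exclusion 3 removes uncontrolled diabetes and hypertension, and exclusion 6 removes thiazides and loop diuretics. This stands and limits the severity.
- **Sampling may defeat the rule.** With draws about two weeks apart, a fast rise could pass both levels between draws, and an added clause would then change nothing. It would help only with slower rises.

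**Conclusion.** The point holds as a low-severity safety improvement. No creatinine-based stop is required when creatinine passes 2.0/2.5 mg/dL in a participant whose baseline is above 0.67 (women) or 0.83 mg/dL (men). At the ordinary baselines tabulated, the gap is 0.1 to 1.1 mg/dL and is entered only after a 2.0- to 2.9-fold rise. Section I plans for 50 people on zonisamide. The share affected cannot be calculated without baseline data, but it is probably small.

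A reader might infer that the protocol leaves participants on a contraindicated drug with nothing to protect them. The documents do not support that: the acidosis stop and the duty to withdraw on clinical grounds both apply, and the study physician has the 2.0/2.5 figures in the same document. A reader might also take required stops above 6.0 or 7.5 mg/dL as the realistic exposure. Those need baselines at the very edge of the numeric limit, which the other exclusions make unlikely and which no document shows anyone to have had. What is missing is narrower: an action tied to an absolute creatinine value.

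**What to change.** In both places where the rule appears (the note to exclusion 4 in Section I and the Zonisamide paragraph of Section M), specify whichever of these comes first:

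- discontinue at a more than threefold rise in creatinine from baseline; or
- hold study drug when creatinine exceeds 2.0 mg/dL (women) or 2.5 mg/dL (men), repeat the test within a stated short window (for example, one week), and discontinue if the repeat confirms it. If it does not, restart at a dose set by the study physician.

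The restart step is needed because Section L reaches 400 mg only by stepwise titration, with maintenance from week 7. Hold-and-confirm is preferable to an immediate stop. A woman admitted at 1.9 mg/dL would cross the limit after a 5% rise (2.0/1.9 = 1.05) and should not lose treatment on one unconfirmed value. Reusing the entry limit is a choice, and the study physician could justify another absolute level.

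The cost is small. Creatinine is already among the safety chemistries, and the Covid-19 procedures already use an outside laboratory, although an on-treatment confirmatory draw would be new. Expect an occasional unscheduled draw, brief dose interruptions and a few more discontinuations. Because treatment is blinded, the rule would apply to all 100 planned participants, not only the 50 on zonisamide. Section L already lets anyone who stops medication remain in assessments and continue Take Control.
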